9.2 Ethics

The appropriate IRB must review the Study Protocol and the Informed Consent Form prior to initiating the study. Any significant modifications to the IRB-approved protocol or informed consent must be made in consultation with the IRB.

9.3 Confidentiality of Subjects

Any information that identifies subjects with respect to this research study will be kept confidential. However, records identifying the subject may be inspected by representatives of the IRB, the Clinical Research Organization (or its designate) if applicable, and/or the FDA. Subjects' identity will remain strictly confidential during all record reviews, as well as in any publication that may result

WIN2023 (v.06feb2023) Page 12 of 14

from this research. Subjects will be identified by study code only; their names will not be used.

9.4 Informed Consent

Informed consent is a process that is initiated prior to the individual's agreeing to participate in the study and continuing throughout the individual's study participation. Appropriate discussion of risks and possible benefits of this therapy will be provided to the subjects. Consent forms describing in detail the study interventions/products, study procedures and risks will be given to the subject and written documentation of informed consent is required prior to starting intervention/administration study product. Consent forms will be IRB approved and the subject will be asked to read and review the document. Upon reviewing the document, the investigator will explain the research study to the subject and answer any questions that may arise. The subjects will sign the informed consent document prior to any procedures being done specifically for the study. The subjects should have the opportunity to discuss the study with their surrogates or think about it prior to agreeing to participate. The subjects may withdraw consent at any time throughout the course of the trial. A copy of the informed consent document will be given to the subjects for their records. The rights and welfare of the subjects will be protected by emphasizing to them that the quality of their medical care will not be adversely affected if they decline to participate in this study.

9.5 Data Handling and Record Keeping

Investigators must ensure that proper source documentation for all study activities are diligently maintained and securely kept. Investigators will transfer all relevant data from source documents to the Case Report Form as stipulated in this Study Protocol and his/her signature on the Case Report Form guarantees completeness and integrity of these data. Investigators will maintain reliable study device dispensing/dosing records and will store study supplies in a secure, locked location. In addition, Investigators will ensure that all study-related source documentation and Case Report Forms will be maintained for a period of two years after the conclusion of the study.

9.6 Direct Access to Source Data/Documents

Investigators must ensure that institutional regulations and the Informed Consent Form clearly permit study-related monitoring, audits, IRB review, and regulatory inspections providing direct access to source data and documents.

10 SUPPLEMENTS

I Prohibited Medications / Wash-Out Periods

SUPPLEMENT I Prohibited Medications / Wash-Out Periods

Use of the following medications (concurrent and contraindicated treatments) are prohibited during the course of the study and appropriate wash-out periods must be respected:

	Medication	Washout
Tonical	Retinoids, antibiotics, BPO, dapsone, bleaching agents	2Weeks washout prior to ∀1

WIN2023 (v.06feb2023) Page 13 of 14

OTC acne medications or bleaching agents	1Week washout prior to V1
Oral Antibiotics for acne	4Weeks washout prior to V1
Oral Retinoids	24Weeks washout prior to V1
Cryotherapy, chemical peels, microdermabrasion	2Weeks washout prior to V1
Laser Resurfacing and dermabrasion	24Weeks washout prior to V1
Investigational Drugs	4Weeks washout prior to V1

WIN2023 (v.06feb2023) Page 14 of 14

Dermatology Life Quality Index (DLQI)

The aim of this questionnaire is to measure how much your skin problem has affected your life OVER THE LAST WEEK. Please circle one response for each question below.

- 1. Over the last week, how itchy, sore, painful or stinging has your skin been?
 - a. Very Much
 - b. A Lot
 - c. A Little
 - d. Not at All
- 2. Over the last week, how embarrassed or self-conscious have you been because of your skin?
 - a. Very Much
 - b. A Lot
 - c. A Little
 - d. Not at All
- 3. Over the last week, how much has your skin interfered with you going shopping or looking after your home or garden?
 - a. Very Much
 - b. A Lot
 - c. A Little
 - d. Not at All
 - e. Not Relevant
- 4. Over the last week, how much has your skin influenced the clothes you wear?
 - a. Very Much
 - b. A Lot
 - c. A Little
 - d. Not at All
 - e. Not Relevant
- 5. Over the last week, how much has your skin affected any social or leisure activities?
 - a. Very Much
 - b. A Lot
 - c. A Little
 - d. Not at All
 - e. Not Relevant
- 6. Over the last week, how much has your skin made it difficult for you to do any sport?
 - a. Very Much
 - b. A Lot
 - c. A Little

WIN2023 (v.06feb2023) Page 15 of 14

- d. Not at All
- e. Not Relevant
- 7. Over the last week, has your skin prevented you from working or studying?
 - a. Yes
 - b. No
 - c. Not Relevant

If "No", over the last week how much has your skin been a problem at work or studying?

- a. A Lot
- b. A Little
- c. Not at All
- 8. Over the last week, how much has your skin created problems with your partner or any of your close friends or relatives?
 - a. Very Much
 - b. A Lot
 - c. A Little
 - d. Not at All
 - e. Not Relevant
- 9. Over the last week, how much has your skin caused any sexual difficulties?
 - a. Very Much
 - b. A Lot
 - c. A Little
 - d. Not at All
 - e. Not Relevant
- 10. Over the last week, how much of a problem has the treatment of your skin been, for example by making your home messy, or by taking up time?
 - a. Very Much
 - b. A Lot
 - c. A Little
 - d. Not at All
 - e. Not Relevant

WIN2023 (v.06feb2023) Page 16 of 14

WIN2023 (v.06feb2023) Page 17 of 14

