1 GENERAL INFORMATION

1.1 Introduction

Acne vulgaris is the most common skin disease in patients with skin of color and second most common in Caucasian population¹. The global prevalence is thought to be as high as 60-80% in individuals 12-25 years of age^{1,2}. However, it is not limited to only teenagers but also to adults, especially adult females³. The pathogenesis of acne is multifactorial. Genetics may also play a role. The treatment pathway should be directed to different pathogenic factors including, excessive sebum production, hyper keratinization, *P. acnes*, and inflammation^{4,5,6,7,8}.

Winlevi is the first topical anti androgen and sebum inhibitor approved for acne vulgaris. However, we do not have any clinical experience with Winlevi in combination treatment for acne. Acne vulgaris is a multifactorial disease and topical retinoids and Benzoyl peroxide and topical clindamycin products have been mainstay treatments for acne in our clinical practices.

Therefore ,it is reasonable to study Winlevi with Duac gel in combination to emulate real life practice.

References:

- 2. Plewig G, Kligman AM: Acne and rosacea, ed 3. Berlin Springer, 2000.
- 4. Williams C, Layton AM: Persistent acne in women: implications for the patient and for therapy. Am J Clin Dermatol 2006;7:218-290
- 8. Lomholt HB, Kilian M: Population genetic analysis of *Propionibacterium acnes* identifies a subpopulation and epidemic clones associated with acne. PloS One 2010;5:e12277
- 9. Winlevi packge insert

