3 STUDY DESIGN

This is a two-center, open-label pilot study. All study subjects will receive both Winlevi and Duac gel gel at baseline. The duration of the study is 16 weeks and consists of a Screening, Baseline Visit, and five (5) Follow-up Visits at Weeks 4, 8, 12 and 16. The treatment period is 12 weeks and 4 weeks of safety follow up totaling to 16 weeks.

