4 SELECTION AND WITHDRAWAL OF SUBJECTS

4.1 Inclusion Criteria

i. Outpatient, male or female subjects of any race, and at least 12 years of age or older. Female subjects of childbearing potential must have a negative urine pregnancy test result at Baseline (test must have a sensitivity of at least 25mIU/ml for human chorionic gonadotropin) and practice a reliable method of contraception throughout the study:

A female is considered of childbearing potential unless she is:

- postmenopausal for at least 12 months prior to study drug administration;
- without a uterus and/or both ovaries; or
- has been surgically sterile for at least 6 months prior to study drug administration.

Reliable methods of contraception are:

- hormonal methods or intrauterine device in use ≥ 90 days prior to study drug administration;
- barrier methods plus spermicide in use at least 14 days prior to study drug administration; or
- vasectomized partner (vasectomy must be performed 3 months prior to first study drug administration or in the alternative a zero sperm count will suffice)

[Exception: Female subjects of childbearing potential who are not sexually active will not be required to practice a reliable method of contraception. These subjects may be enrolled at the Investigator's discretion if they are counseled to remain sexually inactive during the study and understand the possible risks in getting pregnant during the study.]

- ii. Facial acne IGA score of 3 or 4.
- iii. Able to understand the requirements of the study and sign Informed Consent/HIPAA Authorization forms. Subjects under the legal age of consent in the state where the study is conducted must also have the written, informed consent of a parent or legal guardian.

WIN2023 (v.06feb2023) Page 4 of 14

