4.2 Exclusion Criteria

- i. Female subjects who are pregnant (positive urine pregnancy test), breast-feeding, or who are of childbearing potential and not practicing a reliable method of birth control.
- ii. Allergy or sensitivity to any component of the test medications (Section 5.2).
- iii. Subjects who have not complied with the proper wash-out periods for prohibited medications (Supplement I).
- iv. Medical condition that, in the opinion of the Investigator, contraindicates the subject's participation in the clinical study.
- v. Skin disease/disorder that might interfere with the diagnosis or evaluation of acne vulgaris
- vi. Evidence of recent alcohol or drug abuse.
- vii. History of poor cooperation, non-compliance with medical treatment, or unreliability.
- Exposure to an investigational drug study within 30 days of the Baseline Visit.
- ix. Patients who have demonstrated hypersensitivity (e.g., anaphylaxis) to clindamycin, benzoyl peroxide, any components of the formulation, or lincomycin. (4) Patients with a history of regional enteritis, ulcerative colitis, or antibiotic-associated colitis (including pseudomembranous colitis)

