6.2 Secondary Endpoints

- 1. Percent of total lesion reduction at week 16 compared to baseline
- 2. Percent of inflammatory lesion reduction at week 16 compared to baseline
- 3. Percent of non-inflammatory lesion reduction at week 16 compared to

baseline.

4. Tolerability measures such as, erythema, scaling, dryness, oiliness, burning/stinging and pruritus.

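### Supplement I washes out both Duac ingredient classes but not topical clascoterone (Winlevi), so a current Winlevi user can enter with an on-treatment baseline

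*Combined protocol and SAP*

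**What the plan says.** Prior acne treatment is controlled through one exclusion in section 4.2: "Subjects who have not complied with the proper wash-out periods for prohibited medications (Supplement I"). The control is therefore only as wide as the list in Supplement I. The topical row of that list reads "Retinoids, antibiotics, BPO, dapsone, bleaching agents", with 2 weeks before Visit 1. The other rows cover OTC acne products, oral antibiotics, oral retinoids, procedures and investigational drugs. Clascoterone and topical anti-androgens appear in none of them.

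Section 4.2 also excludes "Exposure to an investigational drug study within 30 days of the Baseline Visit". On severity, section 4.1 asks for "Facial acne IGA score of 3 or 4" and sets no condition on treatment in use when the score is taken. Section 1.1 states that "Winlevi is the first topical anti androgen and sebum inhibitor approved for acne vulgaris", and section 5.2.5 says that commercial product will be used.

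The lesion endpoints in section 6.2 are changes from baseline, for example "Percent of inflammatory lesion reduction at week 16 compared to baseline". The same section lists "Tolerability measures such as, erythema, scaling, dryness, oiliness, burning/stinging and pruritus". On timing, section 3 says: "The treatment period is 12 weeks and 4 weeks of safety follow up totaling to 16 weeks".

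**The concern.** All subjects receive both drugs and there is no control arm, so the subject's own baseline is the only comparator for the lesion endpoints. The wash-out list shows that the sponsor wants that baseline free of other topical acne treatment. It achieves this for Duac but not for Winlevi.

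A patient who used Winlevi up to Visit 1 would have an on-treatment baseline count. Any lesion reduction that Winlevi had already produced would be missing from the measured percent change. Tolerability is affected in two ways. Reactions to the Winlevi component may look milder than in new users, although Duac would still be newly started. An improvement in oiliness could be understated, because section 1.1 describes Winlevi as a sebum inhibitor. The primary endpoint in section 6.1 is IGA status at week 16, not a change. It is exposed only through selection of patients who remain IGA 3 or 4 despite Winlevi.

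**Working it through.** **Step 1: does any rule reach current Winlevi use?**

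| Rule | Reaches prescribed clascoterone? |
|---|---|
| Supplement I, topical row (2 weeks) | No. Section 5.2.2 calls it an androgen receptor inhibitor, which is none of the listed classes |
| Supplement I, OTC row (1 week) | Not named; the study product is a prescription product |
| Supplement I, oral drugs and procedures | No |
| Supplement I, investigational drugs (4 weeks) | No. Section 1.1 describes Winlevi as approved |
| Section 4.2, investigational-study exclusion (30 days) | No. It concerns prior drug studies |
| Section 4.1, severity criterion | No condition on current treatment |
| Section 5.3, concomitant therapy | Limits therapy to what will not interfere with response and requires recording, but sets no wash-out before Visit 1 |

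Duac is clindamycin plus benzoyl peroxide (section 5.2.2), and both classes are in the topical row. Only one of the two study drugs is covered.

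**Step 2: direction and formula.** The plan gives no figure to reproduce and no response sizes, so the values below are assumptions. For one subject let:

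- c = lesion reduction at week 16 from that subject's own untreated count;
- w = the part of that reduction already present at Visit 1 because of Winlevi.

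The Visit 1 count is (1 − w) and the week-16 count is (1 − c), both as fractions of the untreated count.

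Measured reduction = 1 − (1 − c)/(1 − w) = (c − w)/(1 − w)

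Shortfall = c − (c − w)/(1 − w) = w(1 − c)/(1 − w)

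The shortfall is positive whenever w > 0 and c < 1. This does not depend on whether week 16 falls on treatment or 4 weeks after a 12-week treatment period; that only changes the value of c.

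**Step 3: size for one affected subject, c = 60%.** The mean shift is the shortfall divided by n. Section 8.1 gives n = 20 and section 1.2 gives n = 10, so both are shown.

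| w | Measured reduction | Shortfall (points) | Mean shift, n = 20 | Mean shift, n = 10 |
|---|---|---|---|---|
| 5% | 57.9% | 0.05 × 0.40/0.95 = 2.1 | 0.1 | 0.2 |
| 10% | 55.6% | 0.10 × 0.40/0.90 = 4.4 | 0.2 | 0.4 |
| 20% | 50.0% | 0.20 × 0.40/0.80 = 10.0 | 0.5 | 1.0 |
| 40% | 33.3% | 0.40 × 0.40/0.60 = 26.7 | 1.3 | 2.7 |

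In counts: an untreated 50 lesions falling to 20 is a 60% reduction. If Winlevi has already brought the count to 45 at Visit 1, the same end point reads as 25/45 = 55.6%.

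**Step 4: sensitivity to c.** With c = 50% the shortfall runs from 2.6 points (w = 5%) to 33.3 (w = 40%). With c = 70% it runs from 1.6 to 20.0. The w = 40% row is an extreme. A subject must still be IGA 3 or 4 on Winlevi to enter, which makes small w more plausible.

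**Step 5: feasibility of a wash-out.** Section 5.1.1 places Screening up to 30 days before Baseline. A 14-day wash-out fits.

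**The case against.** The strongest reply is that the harm is hypothetical. Nothing in the documents suggests that any subject will enter on Winlevi, and with none the effect is zero. At the more plausible values of w, one such subject moves the mean by less than half a point. This is an open-label pilot with no formal sample size justification and no stated success threshold that such a shift could cross. Concomitant medication is recorded at Screening and Baseline, so with 10 or 20 subjects any such patient would be visible. All of this stands, and it is why the point is minor.

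A second reply is that the direction is not certain. A prior user has longer total exposure and might reach a lower week-16 count than a new user. If the total reduction were 62% with w = 5%, or 64% with w = 10%, the measured value would be 60%, the same as for a new user with a 60% reduction. That is correct for a comparison with new users. The formula here compares the subject with that subject's own untreated count, and on that comparison the direction is fixed.

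Third, nothing in the documents shows that lesion counts return to an untreated level in 14 days. This also stands: the interval is borrowed from the other prescription topicals. Finally, the list is organised mainly by treatment class, so the omission may be incidental. That does not change what the rule admits.

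**Conclusion.** The gap is real. As written, the eligibility rules admit a current Winlevi user with IGA 3 or 4 and take that patient's on-treatment count as baseline. That the rule is missing is certain from the text; the size of the effect is not.

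The lesion bias exists only if such a subject enrols and Winlevi had already lowered the count. It then works against the treatment and cannot create a false signal of efficacy. Under the assumed c = 60% and w = 5% to 10%, it is 2.1 to 4.4 points for that subject, and 0.1 to 0.4 points in the study mean across the two stated sample sizes. Over c = 50% to 70% and w = 5% to 40%, the per-subject shortfall spans 1.6 to 33.3 points, with the upper part unlikely. No size is claimed for tolerability or for the selection effect on the primary endpoint. Severity is minor.

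**What to change.** Add topical clascoterone (Winlevi) to the 2-week topical row of Supplement I. The interval is a choice made to match the other prescription topicals, since the documents give no period specific to clascoterone.

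Supplement I also prohibits the listed drugs during the study, so add the words *other than the dispensed study medication*. Duac's ingredients already need this exception. Record the stop date of any prior Winlevi use at Screening.

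The cost is one drug name and one short clause in an amendment, plus one recorded date. A few current Winlevi users would have to stop for 14 days within the 30-day screening window or not be enrolled. No visit or procedure is added.
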